12.1.3 Safety

Primary analysis is proportion (95% CI) with any adverse events in aerosol group with subcutaneous group;

Secondary analysis will describe frequencies of individual adverse events (proportions with 95% CI).

An interim analysis of safety data will be completed. For this analysis, the DSMB will use data from the first 100 children in each arm to complete 91 days of follow up. This will be done as soon as possible after these data are available.

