6.3.1.2 Sequence generation

The allocation sequence will be computer-generated random numbers, in permuted blocks, generated by an independent statistician. The randomization ratio will be 1:1.

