7.3 Subject withdrawal/discontinuation criteria

- Withdrawal of consent;
- Serious adverse event;
- Any other situation in which the Principal Investigator finds it in the subject's best interest to no longer continue his/her participation in the study.

If this occurs, the subject will be asked to continue with the clinical follow up as per the study protocol but would be excluded from the analysis. Withdrawn subjects will not be replaced.

See section 6.6.

8 Treatment of subjects

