11.2 Sample size

11.2.1 Immunogenicity

Total to be enrolled, 2000. Number available for primary analysis (after loss to follow up), 1600. These numbers are based on the following assumptions:

- Significance 2.5%, one-sided for non-inferiority, 5% two-sided for superiority;
- Non-inferiority margin 5%;
- Power for non-inferiority 90% if true seroconversion is 90% in both arms;
- 20% loss to follow up by day 91.
- Calculate two-sided 95%CI for difference in proportion seropositive at day 91. If lower limit of difference greater than -5% then conclude non-inferiority. If lower limit of difference greater than 0% then conclude superiority.

With 100 children sampled at random from those being followed up, based on a standard deviation of post vaccination titres of 0.43, differences of <1.5 fold in geometric mean titres between aerosol and subcutaneous groups between days 28 and 364 would be able to be detected at a 5% level with 80% power. Smaller differences between days 28 and 91, and 91 and 364 would also be detectable.

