11.2.2 Safety

To estimate proportions with adverse events in aerosol and subcutaneous groups, the sample sizes above give acceptable precision.

Observed proportion	95% confidence intervals		
	N=100	N=800	N=1000
0%	0.00 - 3.6%	-	0.00 - 0.37%
1%	0.02 - 5.44%	0.43 - 1.96%	0.48 - 1.83%
2%	0.24 - 7.04%	1.15 - 3.23%	1.26 - 3.07%
5%	1.64 – 11.28%	3.60 - 6.75%	3.73 - 6.54%

With 1000 infants in each group the precision of estimation of adverse events is:

If no reactions are observed, the upper 95% confidence interval with a sample size of 1000 is 0.37%, or 1 in 270.

With 100 children sampled at random for follow up to 364 days, the precision for estimating the prevalence of rare events is low. If zero events are observed by day 364 the upper 95%CI will be 3.6% (1 in 28).

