The primary efficacy analysis for safety includes all children vaccinated, according to the route of vaccination that they received and with at least one safety assessment.

In addition, we will summarize explicitly any severe reactions or serious adverse events (SAE) in children vaccinated by the wrong route.

11.5 Timing of Analyses:

The primary efficacy analysis will be conducted after the last enrolled participant completes the day 91 follow up visit.

Every 3 months the data will be analyzed and a report will be made available for the DSMB. This report will focus on safety.

11.6 Method for Handling Missing Data:

For the primary efficacy analysis there is no plan to impute data values for participants who do not complete follow up visits.

For the PP dataset, missing values will be treated as missing at random. However, preliminary analyses such as age, sex, baseline immunogenicity distribution will be studied between the two groups to examine the validity of this assumption.

For the assessment of immunogenicity, missing values (e.g. no blood taken) are treated as if they are missing at random. The OD values for blood samples taken outside the specified time limits will be treated as missing values.

Note that missing values at 91 days post-vaccination and at other time points will be considered for further analyses. The missing information will be handled by best and worst case scenario methods. Where blood specimens are taken outside the recommended time interval, these results will still be used.

11.7 Significance Level:

This is a non-inferiority trial and the confidence interval approach will be used to determine the trial outcome. For additional analyses, such as those adjusting for covariates, we will not use a fixed 'statistical significance' level for reasons described by Sterne and Davey Smith (3). For analyses that require the calculation of p values, we will base our interpretation on examination of the effect size, confidence interval and p value.

11.8 Safety:

We will estimate the proportions (with 95% CI) of AE in each arm according to the definitions of the primary and secondary safety outcomes (Refer section 8.7 in the protocol).

SOP VEL 1/1:	Statistical Analysis Plan	Page 10 of 61
September 11, 2012		

11.9 Covariates to be examined:

Covariates of interest are as follows:

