0-30mins						
31 mins to day 14						
Day15-28						
Day29-56						
Day57-91						
Day 92-364*						
Total						

*Applies to Vadu subset only

Table 13.2.1B: Number of AEs reported according to severity in the Subcutaneous group

Time Points		Severity of A		SAE	
	Mild n (% of events)	Moderate n (% of events)	Severe n (% of events)	Total	n (% of events)
0-30mins					
31 mins to day 14					
Day15-28					
Day29-56					
Day57-91					
Day 92-364*					
Total					

*Applies to Vadu subset only

Phase II/III
Clinical Trial

13.3: Causality

Table 13.3.1A: Number of moderate and severe Adverse Events and relationship to vaccination, Aerosol group

	Relationship to Vaccination						
Time Points	Not Related n (% of events)	Unlikely to be Related n (% of events)	Possible n (% of events)	Probable n (% of events)	Most Probably n (% of events)	Insufficient data to assess n (% of events)	Total
0-30mins							
31 mins to day 14							
Day15-28							
Day29-56							
Day57-91							
Day 92-364*							
Total							

*Applies to Vadu subset only

Table 13.3.1B: Number of moderate and severe Adverse Events and relationship to
vaccination, Subcutaneous Group

	Relationship to Vaccination						
Time Points	Not Related n (% of events)	Unlikely to be Related n (% of events)	Possible n (% of events)	Probable n (% of events)	Most Probably n (% of events)	Insufficient data to assess n (% of events)	Total
0-30mins							
31 mins to day 14							
Day15-28							
Day29-56							
Day57-91							
Day 92-364*							
Total							

*Applies to Vadu subset only

Phase II/III	WHO Measles Aerosol Vaccine	Protocol
Clinical Trial	Project	WHO/MAP/IN/002

13.4: Listing of AEs by subject

Table 13.4.1: AE listing by Subject

subject ID(Sex)	Age (Day)	Vaccinat ed Date	AE	Date of AE onset	Days to start AE	Date of AE stops	Duration of AE existence (in days)	Concomitant Medications given for the Visit	AE treatment outcome

Phase II/III	WHO Measles Aerosol Vaccine	Protocol
Clinical Trial	Project	WHO/MAP/IN/002

14.0 Interim Analyses:

An interim analysis of safety data will be completed for this analysis. This includes only safety assessment events reported within 91 days after vaccination, and no laboratory results will be included. The DSMB will use data from the first 100 children in each arm. This will be done as soon as possible after these data are available.

Table 14.0.1: Frequency of all AEs by study group and time since vaccination

	Time since vaccination																	

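### Protocol 12.1.3 limits the interim safety set to children who complete 91 days, while SAP 14.0 sets no such condition; followed as written, the protocol rule can make the interim adverse event rates too low

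*Supplement*

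**What the plan says.** Protocol 12.1.1 announces one interim analysis, for adverse events only. Protocol 12.1.3 defines its sample: "the DSMB will use data from the first 100 children in each arm to complete 91 days of follow up".

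SAP 14.0 describes the same analysis differently: "The DSMB will use data from the first 100 children in each arm". The 91-day limit there applies to events, not to children: "This includes only safety assessment events reported within 91 days after vaccination, and no laboratory results will be included".

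For the main safety analysis, SAP 11.4 uses a set that "includes all children vaccinated, according to the route of vaccination that they received and with at least one safety assessment".

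Protocol 7.3 makes withdrawal of consent, a serious adverse event, or the investigator's judgement grounds for withdrawal. Such a child is asked to carry on with clinical follow-up "but would be excluded from the analysis. Withdrawn subjects will not be replaced". The sentence is not confined to immunogenicity.

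Other safety information goes to the DSMB as well. Protocol 8.7.3 and 8.7.6 provide for reports of severe and serious events. Protocol 8.7.6 also promises quarterly summaries of all adverse events, and 11.5.6 promises quarterly unblinded reports. SAP 11.5 adds a three-monthly report focused on safety, with its tables laid out in SAP Appendix 1.

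**The concern.** The protocol rule selects children on something that happens after vaccination. Completing 91 days requires that the child survived and stayed in contact, and either can depend on how the child fared after the vaccine. A safety table built from completers therefore describes those who did well enough to remain, and its rates can be too low. Each child who leaves is replaced by the next to complete, so the denominator stays at 100 and the table itself gives no sign that anyone was left out.

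The SAP sentence does not carry the completion condition. SAP 4.0 tells the statistician to work to both the protocol and the SAP, which cannot be done here. Nor is completion the trial's own standard for safety, since SAP 11.4 takes every vaccinated child with one assessment.

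At stake are the by-arm adverse event rates in the interim tables (SAP Tables 14.0.1 to 14.0.3). These are the DSMB tables in the SAP that show mild and moderate events by arm.

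**Working it through.** **1. The plan's own figure.** Protocol 11.2.2 gives the precision for 100 children with no events: "If zero events are observed by day 364 the upper 95%CI will be 3.6% (1 in 28"). It is stated for the day 364 subset, but the interim sample per arm has the same size. The exact 95% upper limit for 0 of n is 1 − 0.025^(1/n). With n = 100 this is 3.62%, so the figure is reproduced. The documents give no separate calculation for the interim sample.

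**2. How many children are left out.** Inputs: 100 completers per arm (protocol 12.1.3); 1:1 allocation (protocol 6.3.1.2); "20% loss to follow up by day 91" (protocol 11.2.1). With loss d, the number left out per arm is about 100/(1 − d) − 100.

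| Loss by day 91 | Vaccinated per arm to reach 100 completers | Left out per arm |
|---|---|---|
| 20% (planning figure) | 125 | 25 |
| 10% (assumed) | 111 | 11 |
| 5% (assumed) | 105 | 5 |
| 1% (assumed) | 101 | 1 |

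At 20% that is about 50 children over both arms.

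**3. What this can do to a rate.** The rate among all vaccinated is (1 − d) × (rate in completers) + d × (rate in non-completers). The event rates below are assumptions for illustration; the documents give none. Take 2% in completers, which is what the protocol's interim table would show.

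- d = 20%, non-completers 5%: 0.8 × 2% + 0.2 × 5% = 2.6%
- d = 20%, non-completers 10%: 0.8 × 2% + 0.2 × 10% = 3.6%
- d = 20%, non-completers 20%: 0.8 × 2% + 0.2 × 20% = 5.6%
- d = 5%, non-completers 10%: 0.95 × 2% + 0.05 × 10% = 2.4%

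If non-completers have the same rate as completers, there is no bias. The size depends on both the loss and how strongly leaving is tied to events.

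**4. A single missed event.** Suppose no completer has a given event and one of the 25 omitted children does. The interim table shows 0 of 100, with an upper limit of 3.62%. All 125 vaccinated would give 1/125 = 0.8% (95% CI 0.02% to 4.38%). A fixed set of 100 vaccinated children containing that one event would show 1%, for which the protocol's own table gives an upper limit of 5.44%.

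**5. Which events can go missing.** Consider a moderate, expected reaction in a child lost at day 10. Under protocol 12.1.3 it is not in the interim tables. SAP Appendix 1 tabulates serious, unexpected and severe events only, so it is not in those quarterly tables either. It could appear in the quarterly summary of all adverse events promised in protocol 8.7.6, but the SAP lays out no table for that summary. Reasons for discontinuation by arm are in SAP Table 11.12.5.3, which is neither an interim table nor part of Appendix 1.

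**The case against.** The case on the other side has four parts.

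*The DSMB is not dependent on this table.* This stands. Severe and serious events are reported individually, the DSMB makes the final classification of each, and quarterly reports are not confined to completers. A reader might infer that deaths or serious reactions in early leavers are hidden, or that this is the only by-arm look at all adverse events. The documents support neither reading, given protocol 8.7.3, 8.7.6 and 11.5.6.

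*No decision rule uses the interim rates.* This also stands. Protocol 6.6 and 11.3 and SAP 15.0 tie termination to a single attributed event, not to a proportion among 100 children.

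*The SAP is the later document and may govern.* If it does, the completer rule falls away. But neither document says which prevails, and SAP 14.0 does not say what the first 100 are counted by (enrolment, vaccination or completion). If it is only shorthand for the protocol, the selection remains. On either reading the text needs settling. The DSMB charter listed under Appendix 2 is not shown and may define the set; the mismatch between the two documents shown would still need correcting.

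*The size is uncertain.* This stands. The 20% is a planning allowance from the immunogenicity sample size, and protocol 8.9 sends field workers after children who miss clinic visits, so actual loss may be much lower. A reader might also infer that the rule hides a difference between arms. Because the trial is open-label, withdrawal after a reaction could differ by arm, but nothing in the documents shows that it would.

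Nor is this the only place where safety data depend on retention. Protocol 7.3 removes withdrawn children from analysis in general terms, so correcting 12.1.3 alone would leave a contradiction.

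**Conclusion.** Wrong as written, with limited reach. The protocol's interim safety set is conditioned on reaching day 91, the SAP's is not, and protocol 7.3 would drop withdrawn children as well. Under the protocol wording the interim by-arm rates can be too low, with about 25 children per arm omitted at the planned 20% loss and about 1 to 11 per arm at an assumed 1% to 10%. Whether the rates are in fact too low depends on events being commoner among those who leave, which is plausible because a serious adverse event is itself a ground for withdrawal, but is not quantified in the documents.

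The defect concerns the interim rates, mainly for mild and moderate events. The completion rule in 12.1.3 does not touch the final safety set in SAP 11.4, although the 7.3 exclusion conflicts with that set until it is reconciled.

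**What to change.** - In protocol 12.1.3 and SAP 14.0, use the same definition: the first 100 children vaccinated in each arm, with all adverse events up to day 91 or last contact, whichever comes first.
- Run the analysis when the last of these children has reached day 91 or has left the study.
- Add to the interim tables, by arm, the numbers who died, were withdrawn or were lost, with reasons. The layout of SAP Table 11.12.5.3 can be reused.
- In protocol 7.3, state that exclusion of withdrawn children from analysis does not apply to safety analyses, so that it agrees with SAP 11.4 and the new interim set.

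The cost is a sentence or two in each section and one small table. There is no delay: the 100th child vaccinated in an arm reaches day 91, or leaves, no later than the arm accrues its 100th completer, apart from shifts of a few days within the visit window. The zero-event upper limit stays at 3.6% because n is still 100.

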12.2 Contingency plan in the event of confirmed measles cases and outbreaks

Measles cases occurring in trial participants would permit to examine directly the relative vaccine efficacy of aerosol and subcutaneous measles vaccination. Natural boosting of vaccinated individuals may affect the primary outcome of seropositivity at day 91.

If measles cases or outbreaks are detected by the surveillance system we will take the following special steps.

1. Support the implementation of routine Government of India activities for the investigation of cases and control of outbreaks, as appropriate Field Guide -Measles Surveillance & Outbreak Investigation Guidelines (2005) Government of India, Department of Family Welfare New Delhi).

- 2. Document all the confirmed measles cases among the children enrolled in the trial or in their households.
- 3. Set up an alternative statistical analysis plan addressing the following elements:

- Consider those infants confirmed as measles cases (laboratory confirmation) who had day 91 samples taken prior to their date of onset of measles to have unaffected day 91 results.
- Assume that all confirmed measles cases (laboratory confirmation) occurred among sero-negative infants and class them as such in the analysis (and class non-cases according to their ELISA/PRNT sero-status).
- 4. If an outbreak is confirmed prior to completion of the recruitment period or the last day 91 follow up, then the recruitment period will be extended after the outbreak to reach the estimated sample size of 2000 eligible children not confirmed as measles cases.
- 5. If an outbreak is confirmed in Vadu DSS after 91 day follow up is completed but prior to the completion of the long term (day 364) follow up, there will be no attempts to recruit additional children and they will be analysed as described in point 3 above

13 Direct access to Source Data/Documents documents

The investigator will provide written agreement that the investigator /institution(s) will certify that the monitors, the auditors, the Ethics Review Committee members DSMB members and, the regulatory authority representatives (DCGI) will be granted direct access to his original direct access to source data/documents and medical records for verification of clinical trial procedures and/or data, without violating the confidentiality of the subject, to the extent permitted by the applicable laws and regulations in India.

14 Quality control and quality assurance procedures

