OPV III	2113512	2034476	96	2150681	2084555	92	2055735	2049333	100	2093721	2072128	99	2098904	1595884	76	1974375	1476641	75
BCG	2113512	2127471	101	2150681	2173105	94	2055735	2164062	105	2093721	2139148	102	2098904	1664981	79	1974375	1633207	83
Measles	2113512	1978350	94	2150681	1958080	90	2055735	1997355	97	2093721	1984167	95	2098904	1516299	72	1974375	1472809	75
DPT (B)	2106328	1935233	92	2148636	1972534	92	2126485	1947308	92	1703089	1869012	110	2014740	1447327	72	2253480	1462570	65
OPV(B)	2106328	1949264	93	2106328	1974875	92	2126485	1953872	92	1703089	1874653	110	2014740	1442111	72	2253480	1408211	62
DT	2180871	1957099	90	2219884	1900518	86	2329009	2064416	89	2301437	2150579	93	2458596	1724040	70	2467968	1539717	62
TT (10)	2330045	2034823	87	2371691	2067594	87	2329009	2066254	89	2492831	2226557	89	2237233	1776657	72	2467968	1492166	60
TT(16)	2150421	1875999	87	2189255	1822229	83	2126485	1922415	90	2311947	2085794	90	2244801	1585178	71	2253361	1301775	58
TT (M)	2402459	2261068	94	2444708	2143589	87	2355495	2092637	89	2398739	2061763	86	2405384	1723124	72	2254436	1246894	55

Table 2: Measles immunization coverage 2002-2007, Maharashtra State

Source: http://www.maha-arogya.gov.in/programs/nhp/mchimmunisation/performance.htm

Table 3: Immunization coverage Pune district (1996-2004)												
YEAR	BCG	DPT III	POLIO	MEASLES								
1996-1997	105	98	97	93								
1997-1998	103	98	99	100								
1998-1999	104	102	101	99								
1999-2000	110	103	103	96								
2000-2001	100	102	102	96								
2001-2002	104	100	100	99								
2002-2003	83	79	79	77								
2003-2004	55	51	51	54								

Immunization coverage for Pune district as described in Table 3 (below).

Source: http://www.maha-arogya.gov.in/projectandschemes/basic/achievements.htm

Measles is endemic in this State. There is no current active surveillance of measles cases. Reported figures include mainly data from Government hospitals. The state government is currently undertaking a project on integrated communicable disease surveillance.

Table 4, summarizes the number of cases of vaccine preventable diseases reported during the period 2002-2008.

	Surveillance of Vaccine Preventable Diseases													
Years	Diph	theria	Per	tussis	N.I	N.N.T. TB (TB (Child)		asles	Po	olio	TETANUS (O)	
	Cases	Deaths	Cases	Deaths	Cases	Deaths	Cases	Deaths	Cases	Deaths	Cases	Deaths	Cases	Deaths
2002- 03	27	2	8	0	8	2	803	22	1704	3	4	0	70	13
2003- 04	27	4	1	0	9	4	536	3	2136	30	3	0	69	14

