8.8 Measles surveillance in the study area

A surveillance system is to be established (as an entity separate from the trial) in the entire blocks containing the trial areas. It will be established as described in the WHO Best practices for measles surveillance⁴⁹ and in the Field Guide -Measles Surveillance & Outbreak

Investigation Guidelines⁵⁰ (2005) Government of India, Department of Family Welfare New Delhi.

It is expected that this surveillance system will be operational before the start date of the trial.

The primary purpose of measles surveillance will be to detect, in a timely manner, all areas in the trial whether the measles virus is circulating. Surveillance will be undertaken with support from the Immunization Programme of the State of Maharashtra and with the National Polio Surveillance Project in India. The surveillance system will involve the following:

- All the health facilities/health providers in the study area will be trained to implement timely notification of clinically diagnosed measles (probable) cases will be promoted to detect cases and outbreaks. A designated surveillance medical officer (SMO) will conduct monthly active searches in the registry files (outpatient and inpatient records) to ensure all probable measles cases are reported. All measles outbreaks will be serologically confirmed to differentiate them from other fever and rash outbreaks. The surveillance data should be analysed at all levels to determine and improve the immunization strategies.
- In addition, **during the home and clinic visits** the field workers, medical doctors and nurses will solicit information on the presence of cases of rash and fever illness in the household and in the neighbourhood where the infants enrolled in the trial reside. Any probable case will be reported to the designated SMO for it investigation as per the Field Guide -Measles Surveillance & Outbreak Investigation Guidelines.

Every confirmed case of measles (i.e. laboratory or epidemiological confirmation) and any confirmed outbreak in the study area or surrounding areas will be reported within 24 hours to the Principal Investigator by the State of Maharashtra EPI Manager and by the designated SMO. All confirmed measles cases will be managed according to the National guidelines including the administration of Vitamin A.

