9.1 Primary outcome

Measles seropositivity at day 91 post-vaccination.

Measles seropositive specimens are:

• specimens tested by Enzygnost Anti-measles-virus/IgG (Dade-Behring, Marburg, Germany) enzyme-linked immunosorbent assay with optical density signal ≥ 0.1 , or

specimens tested by Enzygnost with optical density signal < 0.1, that are subsequently tested by plaque reduction neutralization test with a result of \geq 120 mIU/ml measles antibody titre.

For further details, please see Sample processing (HPA 1/1, WHO 2/1, WHO 3/1, WHO 4/1), Measurement of outcomes (SOP HPA 5/1, HPA 6/1, HPA 7/1)

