When a unique study ID has been confirmed the person clicks the 'Randomization' button. The next screen gives the allocation as either, 'AEROSOL' or 'SUBCUTANEOUS'. The system records, in a separate database, the details of study site, child's names, Subject ID number, allocation, date and time of randomization. The randomization database will be maintained in Access as backend. This database will be maintained at the CDMC and the backup will be maintained at the backup server which is kept at the Pharmacology Department Museum (old name: Booshnam Moses Computing Center) (Refer SOP Randomization, No: 05 / 02).

SOP VEL 1/1:	Statistical Analysis Plan	Page 5 of 61	
September 11, 2012			

7.3 Blinding of Laboratory Staff:

Staff at the study sites and participants' parents will know which treatment has been given. To minimize bias in the assessment of immunogenicity outcomes, laboratory staff will not know the treatment allocation or the order of specimens that they will analyze.

In order to blind laboratory staff to the specimen collection time (day 0, day 28 day 91 or day 364) for the subjects, a single digit random number will be generated and concatenated with the subject ID. This is called the Lab Code. Thus a subject will have a unique Lab Code of 5 digits.

The laboratory will be provided with lists of 22 pairs (day 0 and day 91) of specimen Lab Codes, which will be randomly ordered. Similarly, for the specimens of children who will be followed up at day 28 and day 364, the laboratory will be provided with lists of randomly ordered Lab Codes.

8.0 Sample size:

8.1 Immunogenicity:

The sample size for the primary outcome is determined using the confidence interval (CI) approach, considering where the CI for the treatment effect lies with respect to a pre-specified margin of non-inferiority and the null effect (1).

Total to be enrolled, 2000. This number was based on the following assumptions:

- Significance 2.5%, one sided for non-inferiority, 5% for two sided superiority;
- Non-inferiority margin 5%;
- Power for non-inferiority 90% if true seropositivity is 90% in both arms;
- 20% loss to follow up by day 91, leaving 1600 available for primary analysis.

Sample size for immunogenicity subset:

Those selected for additional testing at day 28 or at day 364 will have ELISA and PRNT test results at these time points as well as at day 0 and 91.

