In Figure 11.1.1 non inferiority has been demonstrated for scenarios 1), 2) and 3) since the lower limit of the 95% CI is above -5%. In addition for scenario 3) superiority has been shown because the lower limit does not include 0%. For scenarios 4) and 5) non-inferiority has not been demonstrated and for scenario 5) aerosol is inferior as the upper limit does not include 0%.

Note: Using the Wilson score method, 95% CI will be calculated using SAS software. (Newcombe 1998, Agresti et al 1998)

11.2 Per-Protocol (PP) Analysis Set:

This is the analysis set that will be used for the primary analysis of efficacy. The PP analysis set includes all children with an interpretable result from the blood sample scheduled for 91 days (-7 to +28 days), and without major protocol deviations. Study participants remain in the study up to until the point at which they drop-out or deviate from the protocol (Protocol section 12.0).

Protocol deviations include:

- Study participant incorrectly entered the study, e.g. did not meet age criteria;
- Study participant should have been withdrawn during study but was not;
- Study participant did not receive the vaccine according to the arm to which he / she was randomized;
- Study participant received the wrong dose of vaccine;
- Study participant received a dose beyond the recommended multi-dose vial policy
- Wrong subject ID randomized
- Wrong Subject ID
- Home Visit and Clinic visit on same date
- Visits outside the window period
- Wrong labelling of the CRF
- Wrong labelling of vials
- Informed consent issue

The assessment of long-term immunogenicity in the subset of participants from Vadu, includes children with an, interpretable result from blood sample scheduled for 364 days (-7 to +28 days), and without major protocol deviations.

11.3 Modified Intention to Treat (ITT) Analysis Set:

The 'intention to treat' analysis will be conducted as a secondary analysis. In a noninferiority trial such as this, the intention to treat analysis is more likely than the perprotocol analysis to give a type I error (falsely claiming non-inferiority) because this kind of analysis tends to minimize differences between the two treatments (1).

The ITT analysis set includes assessments up to 91 days (-7 to +28 days) post-vaccination. All study participants will be included in the group to which they were randomized.

SOP VEL 1/1:	Statistical Analysis Plan	Page 9 of 61
September 11, 2012		

11.4 As Treated Cohort Analysis set:

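### The outbreak contingency only partly removes the effect of wild measles on day-91 seropositivity, and no sensitivity analysis covers the infections it leaves in place

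*Supplement*

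**What the plan says.** The primary outcome in Protocol 9.1 is "Measles seropositivity at day 91 post-vaccination". Protocol 4.3.5.3 says of the setting that "Measles is endemic in this State", and the opening of Protocol 12.2 states the consequence: "Natural boosting of vaccinated individuals may affect the primary outcome of seropositivity at day 91".

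Point 3 of 12.2 asks for an alternative analysis plan if surveillance finds cases or outbreaks, and lists what it must address:

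- Infants whose day-91 sample preceded the onset of measles keep their result.
- For the other cases: "Assume that all confirmed measles cases (laboratory confirmation) occurred among sero-negative infants and class them as such in the analysis".
- For everyone else: "class non-cases according to their ELISA/PRNT sero-status".

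Protocol 8.8 uses a wider definition: "Every confirmed case of measles (i.e. laboratory or epidemiological confirmation"). Point 4 of 12.2 extends recruitment to reach 2000 children not confirmed as cases, without the laboratory qualifier.

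SAP Version 3 has no rule for measles cases or outbreaks. SAP 11.2 accepts a "blood sample scheduled for 91 days (-7 to +28 days"), which is day 84 to day 119.

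**The concern.** Two groups of vaccine non-responders fall outside the reclassification: those with measles confirmed only epidemiologically, and those infected without being recognised. If wild virus makes them seropositive before the sample, they count as vaccine successes.

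The first group is foreseeable. Protocol 8.8 describes laboratory confirmation at the level of the outbreak and does not promise a test for every case. Points 3 and 4 of 12.2 also disagree. Under the 8.8 definition, an epidemiologically confirmed infant does not count towards the 2000 in point 4, yet point 3 may score that infant as a success.

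At similar attack rates, the arm with more failures gains more false successes. When aerosol is truly worse, its deficit looks smaller, and that is the situation in which the 5-point margin has to protect the conclusion.

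**Working it through.** **Inputs from the documents.** SAP 8.1 gives "Significance 2.5%, one sided for non-inferiority, 5% for two sided superiority", a 5-point margin, 90% power at 90% seropositivity in both arms, 20% loss and 1600 evaluable. Allocation is 1:1 (Protocol 6.3.1.2), hence 800 per arm. The interval is the Wilson score interval for a difference (SAP 11.1). Non-inferiority is concluded if the lower limit exceeds -5% (Protocol 12.1.2).

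**Input assumed.** r is the share of true vaccine failures in each arm that wild virus turns seropositive and the rule does not reclassify. It is taken as equal in the two arms. The documents give no attack rate or capture rate.

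**The plan's own figure.** The unpooled formula gives n = 2 x 0.9 x 0.1 x (1.960 + 1.282)^2 / 0.05^2 = 757 per arm. With a continuity correction it is 797 per arm, or 1594 in total, and 1594 / 0.8 = 1993 enrolled. This agrees with the stated 1600 and 2000. Power at 800 per arm is 91.5% by the normal approximation and 91.3% by exact enumeration with the score interval. The sample size reproduces.

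**Effect of r on the difference.** With true proportions p_A and p_S, the observed proportions are 1 - (1 - p_A)(1 - r) and 1 - (1 - p_S)(1 - r). Their difference is (1 - r)(p_A - p_S).

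**At the margin** (subcutaneous 90%, aerosol 85%, 800 per arm), by exact enumeration:

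| r | Observed difference (points) | Failures counted as successes (aerosol / subcutaneous) | False non-inferiority |
|---|---|---|---|
| 0% | -5.0 | 0 / 0 | 2.5% |
| 2% | -4.9 | 2.4 / 1.6 | 2.9% |
| 5% | -4.75 | 6 / 4 | 3.6% |
| 10% | -4.5 | 12 / 8 | 5.0% |
| 20% | -4.0 | 24 / 16 | 9.8% |

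Check by hand at r = 10%. The observed proportions are 0.865 and 0.910. SE = sqrt((0.865 x 0.135 + 0.910 x 0.090) / 800) = 1.576 points. The shift is 0.5 points, so z = 1.960 - 0.5 / 1.576 = 1.643, an upper tail of 5.0%.

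**What the existing rule achieves.** Assume 20% of failures are infected. Reclassifying 0%, 30%, 60% or 100% of them gives a false non-inferiority rate of 9.8%, 6.6%, 4.4% or 2.5%. With 10% infected, the figures are 5.0%, 4.1%, 3.3% and 2.5%. Each step of reclassification helps, and the problem is what remains.

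**The case against.** The case for leaving the plan alone is substantial.

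- **The rule is conditional and unfinished.** It applies only if cases or outbreaks are detected, and point 3 lists elements of a plan still to be written. An exposure-based analysis is not ruled out. This stands, but nothing in the documents requires one either, and in an open-label trial the rule should be fixed before the data are seen.
- **Wild virus causes the bias.** A reader might infer that the rule itself pushes the result towards non-inferiority. The documents do not support that: compared with the ordinary day-91 analysis, reclassifying laboratory-confirmed cases reduces the bias.
- **Boosted responders are scored correctly.** A reader might count every natural boost as a false success. An infant who responded to vaccine was already seropositive, so only non-responders turned positive matter.
- **The size is unknown.** The documents report about 500 cases a year for Pune city, though they call this probably a gross underestimation, and State totals of 513 and 341 in the two latest periods. Planned detection is active: household and neighbourhood rash and fever are asked about at visits, and confirmed cases in participants and households are documented. A small r is quite possible.
- **Laboratory-only reclassification can be defended.** Protocol 4.3.2 gives fever in 5-15% and rash in 5% after subcutaneous vaccination. Where parents know the route, vaccine reactions could be labelled epidemiologically confirmed measles. If this made a share f of true responders negative in both arms, the difference would shrink by (1 - f), again towards non-inferiority. So widening the main rule is not clearly an improvement.
- **The SAP offers some help.** Table 17.2.1.1 shows the difference by study site, so a localised outbreak could be set against unaffected sites. That is a description by site with no link to outbreak dates, and it does not replace a pre-specified analysis.

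**Conclusion.** The point holds as an incomplete correction. If measles circulates before the day-91 sample and aerosol is truly worse, the share of failures left unreclassified shrinks the observed deficit by (1 - r) and lifts the false non-inferiority rate at the margin above 2.5%: about 2.9% at r = 2% and 5.0% at r = 10%. This assumes 800 per arm, 90% against 85%, and equal r in the two arms.

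With no circulation there is no effect, and with equal failure rates there is no bias in the difference. A reader might take the larger values of r as the expected inflation, but the documents give no attack or capture rate to support that. The gap is worth closing because the protocol itself names the threat and the surveillance data needed are already planned.

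**What to change.** 1. **Add an exposure-based sensitivity analysis** of the primary difference to Protocol 12.2 point 3 and to the SAP. Exclude, in both arms, every infant resident in a confirmed-outbreak village at any time between vaccination and the day-91 sample. Fix the geographical unit in advance and make it smaller than the block: the outbreak triggers in 8.8 work mainly by block, and the five districts tabulated in 4.3.5.4 lie in only three blocks, so exclusion by block could remove much of the sample. Exclusion depends on place and dates, not on arm or serology, so with individual randomisation it is neutral between arms.
2. **Reconcile the meaning of a confirmed case** in 12.2 points 3 and 4 with 8.8. Keep the laboratory-based rule as the main contingency analysis. Handle epidemiologically confirmed cases with onset before sampling in a further sensitivity analysis, stating in advance whether they are excluded or classed as seronegative. Vaccine-related fever and rash are the reason not to move them into the main rule.

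The cost is some wording and two extra analyses on surveillance data already planned. The exposure-based analysis will have fewer infants and a wider interval, and it cannot reach infections outside detected outbreak villages.
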